### **3.3 Study Measures**

3D photogrammetry imaging of each subject at the pre-determined time points will be obtained using the VECTRA M3 (Canfield Scientific, Inc., Fairfield, NJ). This allows for dynamic measurements of facial strain. Each subject's face will be measured along lines of tension when the face is in the relaxed and then frowning. Each facial animation will be recorded as an image. Three-dimensional coordinates will be

CONFIDENTIAL

calculated to generate each subject's topographic configuration, displacement, and surface strain of each detected point on the surface of the face relative to its original reference image.

### ***3.4 Study Endpoints***

#### **3.4.1 Primary Study Endpoint**

The primary endpoint is to quantify the change in dynamic strain of the glabella area after injection of four neuromodulators using 3D facial imaging measurements over time.

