## Study Summary

Title	A Randomized Prospective Evaluation of Four Injectable Neuromodulators in the Glabella Area: Randomized Controlled Trial
Short Title	Glabella 4 Toxin Study
IRB Number	849045
Protocol Number	NCT05167864
Methodology	Randomized Control Trial
Study Duration	18 months
Study Center(s)	Single-center.
Objectives	To quantify the dynamic strain of four commonly available neuromodulators injected in the glabellar area over time as well as correlate patient satisfaction to the change in dynamic strain over time.
Number of Subjects	Approximately 140
Main Inclusion and Exclusion Criteria	
Inclusion criteria:
 

1) Women ages 30-65

2) No neuromodulator treatment within 12 months

3) Have not undergone cosmetic procedures to the upper face above the malar region (cheekbone area).

 
Exclusion:
 

1) Men

2) Patients who have previously been treated with a neuromodulator<12 months

3) Over 65 or under 30 years of age

4) Those with a prior known condition that affects facial animation (such as stroke, palsy),

5) Cannot be actively taking blood thinners,

6) Presence of eye ptosis

7) Autoimmune disease

CONFIDENTIAL

Intervention	Randomization to one of four neuromodulator glabellar injections: 1) onabotulinumtoxinA 2) abobotulinumtoxinA 3) incobotulinumtoxinA 4) PrabotulinumtoxinA
Statistical Methodology	Descriptive statistics will be used to describe variables of interest. Fischer's exact test and Chi-square will be used to compare categorical variables, and linear regression will be used for continuous variables.
Data and Safety Monitoring Plan	PI will oversee the study, protocol, and data monitoring and storage.

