## **2 Study Objectives**

The overall study object is to quantify the dynamic strain of four commonly available neuromodulators using 3D imaging as well as other potential physical measurements differences over time.

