### **2.1 Primary Objective**

To compare the efficacy of four commonly available neuromodulators using 3D imaging to quantify dynamic strain measurements

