#### **3.4.2 Secondary Study Endpoints**

- 1) Quantify the change in the dynamic strain of the glabella area after injection between the four neuromodulators
- 2) Quantify the change of dynamic strain measurements of each facial animation over time.
- 3) Correlation of satisfaction as determined by the FACE-Q to the degree of dynamic strain overtime

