#### **6.2 Statistical Methods**

The primary analysis will be done using chi-squared testing and Fischer's exact test for categorical variables, where applicable, and the paired t-test for continuous variables. Analysis is preformed blinded at the end of the study. There is no interim analysis.

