##### **6.3.2 Analysis of Primary Outcome of Interest**

The primary analysis will be done using chi-squared testing and Fischer's exact test for categorical variables, where applicable, and the paired t-test for continuous variables.

CONFIDENTIAL

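### The primary objective is to compare four products, but the only primary test for continuous strain is a paired t-test, which cannot compare them

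*Combined protocol and SAP*

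**What the plan says.** The document is a combined protocol and SAP. Its statements on this point do not line up.

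- **Objective.** Section 2.1 (Primary Objective): "To compare the efficacy of four commonly available neuromodulators using 3D imaging to quantify dynamic strain measurements". The synopsis and the opening of section 2 are weaker: "To quantify the dynamic strain of four commonly available neuromodulators injected in the glabellar area over time" and "The overall study object is to quantify the dynamic strain of four commonly available neuromodulators using 3D imaging".
- **Primary endpoint.** Section 3.4.1: "The primary endpoint is to quantify the change in dynamic strain of the glabella area after injection of four neuromodulators", measured over time. No contrast between products, visit or facial expression is named. Section 3.1 has four follow-up visits (Day 3, 30, 90, 180) and two expressions (relaxed, frowning).
- **Between-product change.** This is item 1 of section 3.4.2 (Secondary Study Endpoints): "Quantify the change in the dynamic strain of the glabella area after injection between the four neuromodulators".
- **Primary analysis.** Sections 6.2 and 6.3.2 name chi-squared and Fisher tests for categorical variables, "where applicable, and the paired t-test for continuous variables".
- **Synopsis.** Fisher's "exact test and Chi-square will be used to compare categorical variables, and linear regression will be used for continuous variables". No model is written out, and it is not called primary.
- **Design.** Each subject is randomised to one of four products in equal allocation (3.1, 3.2).
- **Sample size.** Section 6.1 cites significant decreases from baseline in two of the four products in a previous study. It gives no between-product difference, SD, alpha or power.

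**The concern.** A paired t-test compares each subject with her own baseline. No subject receives two products, so no pairing across products exists. Whether run arm by arm or pooled, the test says nothing about one product against another. The chi-squared and Fisher tests could compare arms, but strain is continuous and no categorical strain outcome is defined.

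If section 6 is followed, the trial can show that strain falls after injection but not whether any product differs from another. Product claims would then rest on within-arm p-values read side by side, or on between-arm tests chosen later. Section 6.2 says "Analysis is preformed blinded at the end of the study". That limits favouring a known product, but it does not stop a visit, expression or pair being picked because it is significant.

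**Working it through.** **The plan's own figure.** The 140 in section 4.2 cannot be re-derived, because no effect size, SD, alpha or power is stated. Only the dropout step can be checked: 140 × 0.85 = 119 expected completers, and 119 / 4 = 29.75 per arm.

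**Assumptions** (not in the documents): two-sided 0.05, normal data, one visit, and differences in units of the SD of change. Pooled df = 119 − 4 = 115.

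**(a) Can the planned test see a product difference?**
The power of a paired t-test in one arm at mean change δ comes from the noncentral t, with noncentrality δ√29.75 and df 28.75.
- At δ = 1.0 the power is 0.9995. With all four products at 1.0 SD, P(all four significant) = 0.9995⁴ ≈ 0.998.
- With one product at 1.8 SD (power ≈ 1), P = 0.9995³ × 1 ≈ 0.999.
- A pooled paired test is significant in about 100% of trials both times.
- For the 3-df between-arm F test, noncentrality = n Σ(μᵢ − μ̄)². For (1, 1, 1, 1.8) this is 29.75 × (3 × 0.2² + 0.6²) = 29.75 × 0.48 = 14.28, giving power 0.891. With equal products the rejection rate is 0.05.
- Simulation (20,000 trials, 30 per arm) agrees: all four paired 0.998 and 0.998; F 0.048 and 0.895.

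**(b) What if within-arm p-values are read across arms?**
With four identical products, each with within-arm power p, the arms split into significant and non-significant with probability 1 − p⁴ − (1 − p)⁴.

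| True change (SD) | p | Split |
|---|---|---|
| 0.53 | 0.80 | 59% |
| 0.68 | 0.95 | 19% |
| 0.81 | 0.99 | 4% |
| 1.0 | 0.9995 | 0.2% |

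**(c) What if between-arm tests are chosen later?**
With equal products (40,000 simulated trials, one visit), at least one of the six unadjusted pairwise tests is significant in 20.4%. Tukey and the global F test each give 5.0%. Taking the best of four visit-specific F tests gives 17.6%, 16.3%, 13.4% and 9.8% at between-visit correlations of 0.3, 0.5, 0.7 and 0.9 (8,000 trials each).

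**(d) What can 140 subjects detect between products?** (80% power, 29.75 per arm)
- One pair: 0.733 SD unadjusted, 0.896 SD with Tukey, 0.916 SD at 0.05/6.
- Global F: 0.711 SD if one product stands apart; 0.871 SD if two are at the extremes and two midway.
- Power at 0.5 SD: 25% for a Tukey pair; 47% and 32% for the two F patterns.
- Baseline adjustment, assuming equal variances and baseline correlation r, multiplies the SD by √((1 + r)/2): 0.806 at r = 0.3 and 0.922 at r = 0.7. So 0.896 SD becomes 0.72 to 0.83 SD.

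**The case against.** The strongest reply is that most of the document fits within-product change: the synopsis objective, the opening of section 2, the primary endpoint, the sample-size rationale and the paired test. On that reading section 2.1 is the odd one out, and rewording it would remove the contradiction. That is logically sufficient. However, it would give up the comparison that four-arm randomisation exists to support and the treatment-selection aim in section 1.1. It also concedes that the text must change.

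The synopsis regression might be meant for the secondary endpoints beside a paired primary test, in which case the two methods differ without strictly conflicting. It still has no stated arm term, visit or alpha, so it does not supply the missing test.

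Four smaller points have some force:
- The effect sizes are all assumed. The 59% split needs modest within-arm power and falls to 0.2% at 1.0 SD, so it is not a forecast.
- Section 3.3 does not identify the reference image. If it is the relaxed face, dynamic strain may be a single frown-versus-relaxed value. Sections 3.1 and 3.4.2 do treat the expressions separately, but no multiplicity figure across expressions is relied on here.
- A single-visit test moves onset and time course to secondary. A joint arm-by-visit test could also control error, so the single visit is partly a choice.
- If the F test and the Tukey pairs both counted as primary evidence, familywise error would be about 5.9%. Making F the only primary test avoids this.

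**Conclusion.** The point holds and must be fixed. The mismatch between objective, endpoint and test is plain in the text and needs no assumption: the stated primary analysis of continuous strain cannot answer the stated primary objective. The sizes do rest on assumptions (two-sided 0.05, 29.75 per arm, one visit, standardised effects). Under these, a 0.8 SD product difference leaves the planned tests essentially unchanged (99.8% against 99.9%), while one global between-arm test would detect it with 89% power. Six unadjusted pairwise tests chosen later would carry about 20% familywise error.

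**What to change.** Amend sections 3.4.1, 3.4.2, 6.1, 6.2, 6.3.2 and the synopsis together.

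1. **Endpoint.** Move between-product change in glabellar dynamic strain from secondary to primary. Define the strain measure, including the expression and reference image. State one glabellar summary per subject, since section 3.3 yields strain at every detected point, and one visit. The sponsor should fix these before unblinding and before any strain result is analysed; because the planned analysis is itself blinded, unblinding alone would be too late a deadline.
2. **Primary test.** For this endpoint, replace the paired t-test with one 3-df between-arm test at that visit, two-sided 0.05. Take it from a longitudinal model with baseline, arm, visit and arm-by-visit terms. Include all randomised subjects with the visits they have, because 15% dropout is expected. ANCOVA at the visit is a sensitivity check. Avoid a visit-average test: products with different time courses could share the same average.
3. **Pairs.** Follow with the six pairwise contrasts under one adjustment, Tukey or Holm, chosen in advance. State that the global test alone is primary.
4. **Secondary.** Report other visits, the other expression and within-arm change with confidence intervals.
5. **Synopsis and 6.1.** Name the same model in the synopsis. In 6.1, say that the cited rationale concerns change from baseline, and state the detectable between-product differences and the low power at 0.5 SD.

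The cost is text only: no new visits, data or subjects. That assumes strain has not yet been analysed, which the documents do not say. The price is sensitivity: the detectable pairwise difference rises from 0.73 SD unadjusted to 0.90 SD with Tukey, some of which baseline adjustment may recover. Product differences at other visits become secondary.

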#### **3.4.2 Secondary Study Endpoints**

- 1) Quantify the change in the dynamic strain of the glabella area after injection between the four neuromodulators
- 2) Quantify the change of dynamic strain measurements of each facial animation over time.
- 3) Correlation of satisfaction as determined by the FACE-Q to the degree of dynamic strain overtime

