##### **5.2.1 Visit 1 (sometimes referred to as the baseline visit)**

Visit 1 involves screening, consent, baseline imaging to measure dynamic strain, randomization, intervention. The subject will be photographed using 3D imaging with multiple facial animations. All pre-procedure images will be evaluated for absolute strain performing two types of facial animation: 1) relaxed, 2) frowning. Following the baseline images, subjects will complete a FACE-Q questionnaire and then randomized to one of the four neuromodulators onabotulinumtoxinA (Botox, Allergan, Irvine, California), abobotulinumtoxinA (Dysport, Ipsen Biopharmaceuticals Inc. Cambridge, MA), incobotulinumtoxinA (Xeomin, Raleigh, NC) or PrabotulinumtoxinA (Jeuveau, Evolus, Newport Beach, California) according to a preset injection plan per FDA approved administration guidelines. The injector will be blinded to the neuromodulator assigned to the subject via randomization at the time of injection in order to decrease any underlying bias during drug administration. The syringes will be documented and prepared by appropriately trained staff.

CONFIDENTIAL

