##### **6.3.1 Baseline Data**

Baseline and demographic characteristics will be summarized by standard descriptive statistics (including mean and standard deviation for continuous variables such as age and standard percentages for categorical variables such as race).

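### The plan compares products on change in glabellar strain but nowhere says the comparison is adjusted for pre-injection strain, so precision may be lost

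*Combined protocol and SAP*

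**What the plan says.** The primary objective (2.1) is "To compare the efficacy of four commonly available neuromodulators using 3D imaging to quantify dynamic strain measurements". The primary endpoint (3.4.1) is worded as a change: "The primary endpoint is to quantify the change in dynamic strain of the glabella area after injection of four neuromodulators". The first secondary endpoint (3.4.2) carries that change into the comparison of products: "Quantify the change in the dynamic strain of the glabella area after injection between the four neuromodulators".

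On method, 6.2 and 6.3.2 name one technique for continuous outcomes, "the paired t-test for continuous variables". The Study Summary names another, "linear regression will be used for continuous variables", without giving its outcome, its factor or any covariate.

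Pre-injection strain will be available. Section 5.2.1 lists "baseline imaging to measure dynamic strain" as part of Visit 1, ahead of randomisation and injection, and adds: "All pre-procedure images will be evaluated for absolute strain performing two types of facial animation". The only use that Section 6 states for baseline data is in 6.3.1: "Baseline and demographic characteristics will be summarized by standard descriptive statistics". Section 6.3 covers control of bias and confounding through blocks of four and a blinded injector. It mentions neither stratification by strain nor a baseline covariate.

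**The concern.** A change score subtracts the whole of a woman's baseline value. That is the most efficient use of baseline only when follow-up strain rises one for one with baseline strain. At any other slope, part of the baseline variation between women stays in the error of the product comparison, and a model with baseline as covariate would remove it.

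Four active products are compared with about 30 completers each, and 6.1 states no effect size, SD or power. The plan therefore shows no margin of precision to give away. The covariate needed to recover the loss is already collected in every woman.

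**Working it through.** **The plan's own figure.** The total of 140 cannot be re-derived, because 6.1 gives no alpha, power, effect size or SD. Only the drop-out step can be checked: 140 × (1 − 0.15) = 119 completers, and 119 / 4 = 29.75 per product.

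**Inputs.** From the documents: 140 women (4.2), 15% drop-out (6.1), four equal arms (3.2). Not in the documents, so assumed and varied: r, the correlation of baseline with follow-up strain, and L, the follow-up SD divided by the baseline SD. Baseline SD is set to 1.

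**Formulas.**
- Variance of the change score: 1 + L² − 2rL.
- Residual variance after baseline adjustment (large samples): L²(1 − r²).
- Difference between the two: (1 − rL)². This is never negative, and it is zero only when the slope rL equals 1.
- Ratio of change-score to adjusted variance: 1 + (1/L − r)² / (1 − r²). At fixed r this grows as L falls below 1. It shrinks to 1 at L = 1/r, where follow-up strain is more variable than baseline.
- With L = 1, adjusted variance divided by change-score variance is (1 + r)/2.

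**Equal SDs (L = 1).**

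| r | Change variance | Adjusted variance | Adjusted / change | Unadjusted interval wider by | Completers with adjustment matching 119 without |
|---|---|---|---|---|---|
| 0.3 | 1.40 | 0.91 | 0.65 | 24% | 77 |
| 0.5 | 1.00 | 0.75 | 0.75 | 15% | 89 |
| 0.7 | 0.60 | 0.51 | 0.85 | 8% | 101 |
| 0.9 | 0.20 | 0.19 | 0.95 | 3% | 113 |

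For example, at r = 0.3: √(1/0.65) = 1.24, and 119 × 0.65 = 77.

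**Follow-up less variable than baseline.** Unadjusted intervals are wider by:

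| r | L = 0.7 | L = 0.5 |
|---|---|---|
| 0.3 | 55% | 104% |
| 0.5 | 47% | 100% |
| 0.7 | 43% | 108% |
| 0.9 | 57% | 171% |

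For example, at L = 0.5 and r = 0.5: change variance 1 + 0.25 − 0.5 = 0.75, adjusted variance 0.25 × 0.75 = 0.1875, ratio 0.25, and √4 = 2. At that ratio the change score needs four times as many women for the same precision.

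**Standard error of a pairwise product difference**, √(2 × variance / 29.75), in baseline SDs:
- L = 1, r = 0.3: √(2.80/29.75) = 0.307 unadjusted against √(1.82/29.75) = 0.247 adjusted.
- L = 1, r = 0.9: √(0.40/29.75) = 0.116 against √(0.38/29.75) = 0.113.

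**Small-sample check.** In a simulation with 30 women per arm, the ratio of adjusted to change-score variance was 0.764 against 0.750 by formula (L = 1, r = 0.5), and 0.251 against 0.250 (L = 0.5, r = 0.5). The large-sample formulas are adequate at this size.

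**Choice of outcome.** If follow-up Y is modelled as product effect + bX, with X the baseline, then Y − X is product effect + (b − 1)X. Only the baseline coefficient changes. The adjusted product differences are identical whether follow-up strain or change is the outcome.

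**The case against.** The strongest reply is that the plan is silent, not committed to an unadjusted analysis. A reader might infer that it has chosen to compare products on raw change. The documents do not say that: the regression in the Study Summary could carry baseline strain, and change as an outcome is compatible with adjustment. This stands. The fault is an omission, and the wording of the endpoint in 3.4.2 is not itself at fault.

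A reader might also infer that, because these drugs weaken the frown, follow-up strain must be less variable than baseline and only weakly related to it, so that raw change mostly reflects how hard each woman frowned beforehand. No section supports this. Section 6.1 reports significant decreases in an earlier study and gives no SD or correlation. The pattern could also differ between Day 3 and Day 180. With equal SDs, the baseline share of the change-score error variance is 1 − (1 + r)/2, which is 35% at r = 0.3 and only 5% at r = 0.9.

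Nor is chance imbalance in baseline strain a further harm on top of lost precision. Under randomisation the standard error already reflects it.

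Finally, a paired t-test works within women and cannot compare products, so Section 6 has a larger gap: it sets out no between-product analysis. That is true, and the covariate belongs in whatever model fills the gap. It does not make this point redundant, because filling the gap with an unadjusted test on change would leave the loss in place.

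**Conclusion.** The point holds as an omission that should be repaired. The products are to be compared on change in strain, the only continuous method in Section 6 takes no covariate, the Summary's regression names none, and no section puts the available pre-injection strain to use in that comparison.

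The direction of the loss is certain in large samples: adjustment ties when the slope is exactly 1 and gains otherwise. The size is not known. It runs from negligible (3% wider intervals at L = 1, r = 0.9) to intervals about twice as wide (L = 0.5, r = 0.3 to 0.7), and nothing in the documents says where in that range this trial lies. The consequence is reduced precision, not bias on average.

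**What to change.** In 6.2, 6.3.2 and the Study Summary, state that the between-product comparison at each follow-up visit uses a linear model with product (four levels) as factor and the woman's own pre-injection frown strain as covariate. Either follow-up strain or change from baseline may be the outcome; name one. Report adjusted product differences with 95% confidence intervals.

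Keep change in strain as the stated endpoint. Demoting it to a descriptive summary would alter 3.4.1 for no gain, since the adjusted differences are the same.

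The cost is wording and one degree of freedom: with 119 completers and four product means, 115 residual degrees of freedom become 114. No extra visit, image or participant is needed. The text should be settled before the blinded end-of-study analysis, so that the choice of covariate does not depend on the data.

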### ***7.7 Data Collection and Management***

REDCap will be used to store and maintain the primary study records. The data entered into REDCap will be obtained from the study-relevant patient EMRs. Study personnel will be granted access to this project created in REDCap with each user obtaining individual access authenticated by a login system. Minimal patient identifiers will be collected and stored in the REDCap database. Patient name and date of birth will be collected in REDCap.

Source data will mainly be from the patient's EMR. When the study requires data not normally collected in the patient's EMR, the case report forms will also be the source document. Data from source documents (Appendix 15.4, case report forms (case report forms definition- Appendix 15.5), will be entered into an electronic data capturing system. All source documents should be secure in private spaces with restricted access. After Visit 1 the FACE-Q will be sent electronically to the subject for each follow-up visit via a REDCap survey.

During procurement of data charts will be reviewed in private spaces to ensure the confidentiality of acquired data. Data will be stored for up to 7 years after completion of the last follow-up visit of the last patient randomized. Data may be collected for up to two years following the treatment.

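### Secondary endpoint 3 relates FACE-Q satisfaction to strain without giving the pre-injection FACE-Q score any role; adjust for both Visit 1 measures and reconcile the two wordings of the endpoint

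*Combined protocol and SAP*

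**What the plan says.** Section 3.4.2 lists the third secondary endpoint as "Correlation of satisfaction as determined by the FACE-Q to the degree of dynamic strain overtime". Neither side is called a change, and no coefficient, pairing of visits or covariate is named. The first secondary endpoint in the same list is explicitly a change: "Quantify the change in the dynamic strain of the glabella area after injection between the four neuromodulators".

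The Objectives row of the Study Summary states the aim differently: "correlate patient satisfaction to the change in dynamic strain over time". Strain is a change there, but satisfaction is still a level.

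A pre-injection score exists. Section 5.2.1 says "Following the baseline images, subjects will complete a FACE-Q questionnaire and then randomized to one of the four neuromodulators", and Table 1 marks the FACE-Q on Day 1. Follow-up scores come at Days 3, 30, 90 and 180; Section 7.7 says "After Visit 1 the FACE-Q will be sent electronically to the subject for each follow-up visit via a REDCap survey".

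Section 6 does not mention the FACE-Q. Section 6.2, repeated in 6.3.2, says "The primary analysis will be done using chi-squared testing and Fischer's exact test for categorical variables, where applicable, and the paired t-test for continuous variables". The Study Summary adds that "linear regression will be used for continuous variables", without naming an outcome or predictor. The only stated use of baseline data is in 6.3.1: "Baseline and demographic characteristics will be summarized by standard descriptive statistics".

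**The concern.** A woman's follow-up satisfaction depends partly on how satisfied she was before the injection, and her follow-up strain partly on how strongly she frowned before it. Endpoint 3 is a comparison across women, not between arms, so randomisation does not balance these differences out.

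There are two consequences. If satisfaction and strain were already related before treatment, part of that relation persists to follow-up and can be taken for a link with strain reduction. If they were not related, the carried-over satisfaction is unexplained variance that weakens the test. Both arise at a single visit with one pair of values per woman, so the issue is separate from how repeated visits are handled. Patient satisfaction is a named objective in the Study Summary, and the score that would address the problem is already scheduled.

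**Working it through.** **Inputs from the documents.** 140 women (4.2) and 15% drop-out (6.1), so 140 × 0.85 = 119 completers. The documents give no target correlation, power or significance level for endpoint 3, so there is no planned figure to reproduce. A two-sided 5% test is assumed.

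**Assumed inputs.** One follow-up visit; all measures scaled to unit variance. S0 and F0 are Visit 1 strain and FACE-Q, with correlation c. Follow-up strain is S1 = a·S0 + √(1−a²)·e, and follow-up satisfaction is F1 = b·F0 + g·e + noise. Here a and b are the persistence of each measure, e is the new part of strain (unit SD), and g is the true link. The documents supply none of these values.

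**Rejection probability.** With z = atanh(|r|)·√(119 − 3 − k) and k covariates, the probability is 1 − Φ(1.96 − z) + Φ(−1.96 − z).

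**No treatment link (g = 0).**
- Level against level (3.4.2): r = a·b·c.
- Level against strain change (Study Summary): r = −b·c·√((1−a)/2).

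| c, a, b | level v level: r, rejection | level v change: r, rejection |
|---|---|---|
| 0, any, any | 0, 5% | 0, 5% |
| −0.2, 0.5, 0.5 | −0.050, 8% | +0.050, 8% |
| −0.3, 0.5, 0.6 | −0.090, 16% | +0.090, 16% |
| −0.3, 0.6, 0.6 | −0.108, 22% | +0.081, 14% |
| −0.4, 0.7, 0.7 | −0.196, 57% | +0.108, 22% |

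Worked example, last row: r = 0.7 × 0.7 × (−0.4) = −0.196; z = 0.1986 × 10.77 = 2.139; rejection = 1 − Φ(−0.179) = 0.571. Simulation of 6,000 trials per case agrees to within about 2 percentage points (the level-against-change maximum came out at 21% to 22%). Adjusting for F0, or for F0 and S0, gave about 5% in every case.

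**Real link (g = −0.25, c = 0, a = 0.5).**
- Unadjusted, either wording: r = −0.25 × √0.75 = −0.2165, power 66%.
- Adjusted for F0: r = −0.2165/√(1−b²). Power is 73% at b = 0.4 and 92% at b = 0.7.
- Adjusted for F0 and S0: r = −0.25/√(1−b²). Power is 85% at b = 0.4, 93% at b = 0.6 and 97% at b = 0.7 (97% to 98% simulated).

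**Check with a different model.** Suppose each measure is a lasting trait plus visit-to-visit error, with the trait accounting for 0.5 to 0.8 of the variance, and the response to treatment is unrelated to the traits. With no true link and a trait correlation of 0.3 to 0.5 in size, level against level rejects in 21% to 98% of trials. Level against strain change rejects in about 5%. Adjusting for both error-prone baselines leaves 5% to 13%.

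**The case against.** **The plan is silent; it does not exclude the baseline score.** This stands. A reader might infer that the protocol has chosen a raw correlation and ruled out the Visit 1 score. No sentence says so: the endpoint's reference to time could include Day 1, and the linear regression in the Study Summary could carry a covariate. What the documents support is that the score is given no role. That is still worth correcting, because a better analysis of data already scheduled can be named now.

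**The largest figure is a corner case.** Also true. The 57% needs the strongest assumed baseline correlation and the highest persistence together, and it applies only to the 3.4.2 wording. With no baseline link the test holds its 5%. Under the Study Summary wording the spurious correlation is smaller and has the opposite sign (more satisfied women showing less reduction), and in the lasting-trait model it vanishes.

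**A real link would be hidden.** A reader might infer this, but it is mostly lost precision: 66% against 85% to 98%. Near-concealment appeared in the lasting-trait model only when women with more strain were assumed to be the more satisfied (trait correlation +0.5). There, level-against-level power fell to 11% to 39%, against 94% to 100% for change against change. Nothing in the documents suggests that direction.

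**Change against change might be better.** It held 5% in the lasting-trait model. In the persistence model above its null correlation is c·√((1−a)(1−b))/2. For c = −0.3, a = 0.5, b = 0.6 this is −0.067, with 11% rejection. Neither method is best under both models.

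**A correlation is a legitimate descriptive aim.** Agreed. All four arms are active and nobody is randomised to a strain level, so no adjustment makes the result causal.

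**Conclusion.** The point holds as a worthwhile improvement to a secondary endpoint. The endpoint and the Study Summary define the association differently, and neither definition, nor Section 6, uses the pre-injection FACE-Q score.

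For 119 women at one visit, with assumed baseline correlations of 0 to −0.4 and persistence of 0.5 to 0.7, the chance of a nominally significant result with no treatment link is about 5% to 57% (level against level) or 5% to 22% (level against strain change). For a real 0.25 SD link with no baseline correlation, strain persistence 0.5 and FACE-Q persistence 0.4 to 0.7, power is about 66% unadjusted and 85% to 98% with both baselines. These ranges show sensitivity to assumptions; they do not predict this trial. The primary endpoint is unaffected.

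**What to change.** First reconcile the Study Summary with 3.4.2. Then state in 3.4.2 and Section 6 that endpoint 3 is the association of the follow-up FACE-Q score with strain, adjusted for the woman's own Visit 1 FACE-Q score and Visit 1 strain, at each visit or within whatever repeated-measures model is adopted. Report the raw correlation as descriptive.

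Once Visit 1 strain is a covariate, follow-up strain and change in strain give the same coefficient and test, because β·S1 + γ·S0 = β·(S1 − S0) + (β + γ)·S0. One model therefore serves both wordings.

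The cost is one sentence in the analysis section and two degrees of freedom, with no new data. Any woman without a Visit 1 FACE-Q drops out of this analysis. Baselines measured with error leave a small residual association (5% to 13% rejection in the check above), and the text should say that the result is an association.
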